11. STATISTICS

11.1 Statistical analysis

The null hypotheses being tested are:

- cerebral haemodynamic parameters, including CBFv and ARI, do not differ between baseline recordings and during performance of squat-stand manoeuvres
- cerebral haemodynamic parameters, including CBFv and ARI, do not differ between TIA patients and HC

All data will be tested for normality prior to statistical testing using Shapiro-Wilks. Categorical data will be reported as absolute number and percentages. Continuous data will be plotted and assessed for normality; normally distributed continuous variables will be described as mean (SD) and continuous variables with skewness as median (IQR). Statistical testing for differences between HC and TIA groups will be by two-way ANOVA for continuous, parametric data, Friedman 2 way analysis of variance for continuous, non-parametric data, and Chi-Square for nominal data.

Data will be recorded in Microsoft Excel. Statistical analyses will be performed using the latest versions of SPSS for Windows or Statistica, and graphs will be produced using the latest version of Statistica.

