such as bilateral thigh cuff inflation to suprasystolic blood pressure and their simultaneous release, lower body negative pressure, and the cold pressor stimulus (placing a hand in ice water). These can be uncomfortable for participants. More recently, squat-stand manoeuvres (SSMs) have also been shown to produce large changes in BP and thus CBFv [Claassen et al 2009a, Smirl et al 2015, Barnes et al 2017]. Squatting induces a rapid but transient rise in BP with its peak after approximately 2-3 seconds (s). This increase in BP has been attributed to a sudden increase in cardiac output from increased venous return from the lower limbs. The subsequent reduction in BP on standing up has been attributed to a combination of reduction in peripheral vascular resistance and a reduction in cardiac output due to rapid return of central blood volume to the lower limbs [Smirl et al 2015]. SSMs can be more comfortable for participants and are arguably more representative of physiological BP challenges in daily life, e.g. bending down to pick something up from the floor and standing up after tying a shoelace, than those other BP challenges detailed above. When SSMs are performed repeatedly, large and periodic changes in BP and CBFv are created. SSMs have been shown to be safe and well tolerated in various populations including heart transplant recipients [Smirl et al 2014], young and old healthy controls [Oudegeest-Sander et al 2014, Barnes et al 2017], and patients with Alzheimer's dementia [Claassen JA et al 2009b]. It has recently been shown that reliable CA data can be obtained from as few as three SSMs [Barnes et al 2018].

The proposed study will investigate and compare the beat-to-beat CBFv changes observed during performance of a SSM protocol in 20 participants with acute (within 7 days) TIA and 20 HC. The proposed study will also investigate whether performance of a SSM is associated with differences in other beat-to-beat cerebral haemodynamic parameters, specifically autoregulation index (ARI), between participants with acute (within 7 days) TIA and 20 HC. In doing so, it is hoped that we will be able to establish if CA is impaired in patients with TIA.

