5. OBJECTIVES

5.1 Primary Objective

To determine the beat-to-beat cerebral blood flow velocity (CBFv) of both TIA and HC subjects during performance of a SSM.

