6.2 Primary and Secondary Endpoints/Outcome Measures

This is not an intervention study, and therefore it would not be appropriate to assess classical primary and secondary outcome measures such as death and disability for this study. However, we intend to evaluate the following relevant outcomes:

- a) The number of participants recruited
- b) The number of participants able to comply with the full measurement protocol
- c) The number of measurements rejected because of aspects related to data quality during the analysis protocol, with recorded reasons
- d) Overall, the number of recruited subjects in whom values for the following parameters can be derived:
 - % change of cerebral blood flow velocity (CBFv) at baseline in response to performance of a squat-stand manoeuvre
 - Autoregulation index

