8.5 TCD Assessment

For all subjects, all assessments will be undertaken in a dedicated cardiovascular research laboratory at Leicester Royal Infirmary (LRI), which is at a controlled temperature (20-24°C) and is free from distraction. Participants will be asked to refrain from heavy meals, strenuous exercise, alcohol, smoking and caffeine if possible for four hours prior to attending the research laboratory. Baseline brachial casual BP will be measured using a validated UA767 BP monitor. Beat-to-beat non-invasive BP will be recorded continuously using the Finometer cuff device (Finapres Medical Systems; Amsterdam, The Netherlands) attached to the middle finger of the right hand which will be supported in an arm sling. R-R interval will be recorded using a 3-lead electrocardiogram (ECG). Respiratory rate will be recorded, and end-tidal partial pressure of carbon dioxide (EtCO₂) will be monitored using small nasal cannulae placed at the base of the nose (Salter Labs, ref 4000) attached to a capnograph (Capnocheck Plus) to monitor the breathing. A tilt sensor will be attached to the thigh of the participant's right leg by means of a Velcro strap to measure the efficiency and angle of the squatting motion. Simultaneous bilateral insonation of the middle cerebral arteries (MCAs) will be performed using TCD with 2MHz probe using a DWL Doppler box, with the subject either sitting or lying supine on a couch (in the case of difficult to insonate windows). The vessels will be located via the temporal bone window, and identified as the MCAs by their waveform, depth, velocities, and direction of flow. All parameters will be simultaneously recorded onto a computer software system (PHYSIDAS), providing data for subsequent off-line analysis. A head frame will be used to secure the ultrasound probes in position and to minimise their movement. Once satisfactory signals have been obtained, four recordings will be made:

- 1) A 5 minute baseline recording during which the participant sits quietly with their eyes open
- 2) A 6 minute recording during which the participant sits for 1 minute before standing and remaining standing quietly with their eyes open for 5 minutes

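### Section 11.1 states no hypothesis or named test for whether the CBFv response to the squat-stand manoeuvre differs between TIA patients and healthy controls

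*Combined protocol and SAP*

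**What the plan says.** Section 11.1 lists two nulls, both about cerebral haemodynamic parameters including CBFv and ARI. The first is that they "do not differ between baseline recordings and during performance of squat-stand manoeuvres"; it names no group. The second is that "cerebral haemodynamic parameters, including CBFv and ARI, do not differ between TIA patients and HC"; it names no recording.

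On the test, section 11.1 says: "Statistical testing for differences between HC and TIA groups will be by two-way ANOVA for continuous, parametric data". Friedman's analysis is the non-parametric alternative. No factors, repeated-measures term, interaction or dependent variable are named.

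The aim is worded differently elsewhere. Section 4 says: "The proposed study will investigate and compare the beat-to-beat CBFv changes observed during performance of a SSM protocol", in 20 TIA participants and 20 healthy controls. Sections 2 and 6.2 name the percentage "change of cerebral blood flow velocity (CBFv) at baseline in response to performance of a squat-stand manoeuvre", but only in a count of participants in whom the value can be derived. The primary objective in section 5.1 is descriptive: "To determine the beat-to-beat cerebral blood flow velocity (CBFv) of both TIA and HC subjects during performance of a SSM".

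**The concern.** Section 4 describes autoregulation as keeping flow roughly constant when perfusion pressure changes. That is a property of the response. CBFv at rest, or averaged over rest and squatting, is a different quantity: two groups can differ in it and respond identically, or agree in it and respond differently.

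If the group null for CBFv is tested as a difference in level, rejecting it does not show a different response to the manoeuvre, and failing to reject it does not show the same response. CBFv is the parameter in the primary objective, so this affects a central comparison. ARI is not affected in this way, because it already summarises the pressure-flow response.

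**Working it through.** **1. The text.** The two nulls use the same phrase for what is compared. In the first, CBFv can only be a level, because a percentage change from baseline cannot itself be compared between baseline and squat-stand. The natural reading of the second null is therefore also a level. The comparison of changes promised in section 4 matches neither null, and no test is tied to the percentage change in section 6.2.

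**2. The plan's own figure.** Section 11.2 cites 11 per group for an ARI difference of 2 units, with 80% power at 5%. No SD is given, so this cannot be reproduced. Solved backwards (normal approximation, two-sided), it implies SD = 2 / [(1.960 + 0.842) × √(2/11)] = 1.67 ARI units. It says nothing about CBFv.

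**3. Illustration.** From the documents: 20 per group and a 5% level (two-sided assumed). Assumed, because the documents give no values: one baseline and one squat-stand CBFv value per person, each with SD 1, and within-person correlation ρ of 0.5 to 0.7. Each contrast is a two-sample t-test on 38 degrees of freedom:

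- Group main effect: person means, SD = √((1+ρ)/2), which is 0.866 at ρ = 0.5 and 0.922 at ρ = 0.7.
- Group × recording interaction: person changes, SD = √(2(1−ρ)), which is 1.000 and 0.775.
- Squat-stand recording alone: SD = 1 at any ρ.
- Noncentrality = difference / (SD × √(2/20)), where √(2/20) = 0.316.

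| Scenario | Contrast | Difference | Noncentrality (ρ = 0.5; 0.7) | Significant |
|---|---|---|---|---|
| Level differs by 0.5 SD, same response | Main effect | 0.5 | 1.83; 1.72 | 43%; 39% |
| | Interaction | 0 | 0 | 5% |
| | Squat-stand only | 0.5 | 1.58 | 34% |
| Same at rest, response differs by 0.7 SD | Main effect | 0.35 | 1.28; 1.20 | 24%; 22% |
| | Interaction | 0.7 | 2.21; 2.86 | 58%; 80% |
| | Squat-stand only | 0.7 | 2.21 | 58% |

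Testing the squat-stand recording alone does as well as the interaction at ρ = 0.5 when only the response differs. It still picks up a pure level difference in 34% of studies.

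**4. Scale of the change.** The model in step 3 is additive. Vessel calibre and insonation angle, which the documents do not discuss, would act on velocity by multiplication and so would also scale an absolute change. As a check, assume resting means of 60 and 52.5 cm/s with SD 15 (a 0.5 SD difference) and an identical mean response of 20% to 40% with SD 4 to 8 percentage points, 20 per group. At a 30% response the mean rises are 60 × 0.30 = 18.0 and 52.5 × 0.30 = 15.75 cm/s, so the absolute changes differ although the responses do not. In simulation the absolute-change test was significant in 13% to about 30% of studies, and the percentage-change test in 5%.

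**The case against.** The strongest reply is that section 11.1 never uses the words main effect or level. Its list of parameters is open, and a TIA versus control test of percentage change would fit the second null and answer the question. A two-way ANOVA with group and recording as factors would also normally print the interaction. This stands to a degree: the plan does not rule out the right analysis. But it does not commit to it either, and a printed interaction is not a pre-specified test. If normality is rejected, Friedman's test ranks recordings within each person and has no group-by-recording term.

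A reader might infer that the planned analysis cannot answer the study's question at all. The documents do not support that. The stated hope is to establish whether autoregulation is impaired, ARI addresses that directly, and its group comparison is sound. The objectives are descriptive and the listed outcomes are feasibility counts.

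A reader might also take 39% to 43% as a false-positive rate. It is not. If the groups truly differ at rest, rejecting a null about level is correct, and only the further step to a difference in response would be wrong. Person-to-person variation in calibre or angle creates a group effect only if the groups differ systematically, and the documents give no figure for that.

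Finally, a reader might suppose that such differences drop out of any within-session change because "A head frame will be used to secure the ultrasound probes in position". A fixed probe keeps the angle constant, but a constant multiplier cancels only in a percentage or log change (step 4). Even percentage change does not isolate autoregulation, since section 8.5 lets participants choose their squat depth and the blood pressure stimulus may vary with it.

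**Conclusion.** The point holds as a gap in specification. The plan promises a between-group comparison of CBFv changes but states no null for it and names no test. The natural reading of what it does state is a comparison of level, and the non-parametric fallback cannot supply the missing contrast. Following section 11.1 as written could therefore miss a difference in response or present a resting difference in its place.

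The direction of this risk follows from the text. Its size does not: the contrast of 22% to 24% with 58% to 80% depends on the assumed 0.7 SD effect, on correlations of 0.5 to 0.7, and on averaging the two recordings. It largely disappears at ρ = 0.5 if only the squat-stand recording is compared. The point is confined to CBFv and should be settled before the data are analysed.

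**What to change.** Restate the group null for CBFv as: the within-person percentage change in CBFv from baseline to squat-stand does not differ between TIA patients and healthy controls. Test it by comparing each person's percentage change between groups, or by the group × recording interaction on log CBFv with recording as a repeated factor. Replace Friedman, for this comparison, with a two-sample rank test on percentage change. Say which recording is the baseline, since section 8.5 provides both a seated recording and standing periods around the squats. Report group differences in absolute CBFv as descriptive, and keep the group comparison of ARI.

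The cost is one reworded hypothesis and one or two analysis sentences. All the data needed are already collected under section 8.5.

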2. SYNOPSIS

Study Title	THE ASSESSMENT OF CEREBRAL HAEMODYNAMICS IN PATIENTS WITH TRANSIENT ISCHAEMIC ATTACK: A TRANSCRANIAL DOPPLER STUDY
Internal ref. no.	UNOLE 0694
Trial Design	Single-centre, prospective, case control study
Trial Participants	Participants with Transient Ischaemic Attack (TIA) and healthy adults (HC)
Planned Sample Size	40 participants in total; 20 participants with TIA and 20 HC
Follow-up duration	N/A
Planned Trial Period	6 months
Primary Objective	To determine the beat-to-beat cerebral blood flow velocity (CBFv) of both TIA and HC subjects during performance of a squat-stand manoeuvre
Secondary Objective	To determine other beat-to-beat cerebral haemodynamic parameters, specifically autoregulation index (ARI), of both TIA and HC subjects during performance of a squat-stand manoeuvre
Outcome Measures	
This is not an intervention study, and therefore it would not be appropriate to assess classical primary and secondary outcome measures such as death and disability for this study. However, we intend to evaluate the following relevant outcomes:
 
 1. The number of participants successfully recruited 2. The number of recruited participants able to comply with the full measurement protocol. 3. The number of measurements rejected because of aspects related to data quality during the analysis protocol, with recorded reasons. 4. Overall, the number of recruited subjects in whom values for the following parameters can be derived: 
 • % change of cerebral blood flow velocity (CBFv) at baseline in response to performance of a squat-stand manoeuvre • Autoregulation index

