11.3 The Level of Statistical Significance

Statistical significance will be set at $p < 0.05$

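### An under-specified normality pre-test chooses the method for each parameter, and a parameter sent to Friedman loses its TIA-versus-control test

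*Combined protocol and SAP*

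**What the plan says.** Section 11.1 (Statistical analysis) sets two null hypotheses for the haemodynamic parameters, including CBFv and ARI. The first is within participant: the parameters "do not differ between baseline recordings and during performance of squat-stand manoeuvres". The second is that they are the same in TIA patients and healthy controls (HC).

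The route to a test begins with a normality check: "All data will be tested for normality prior to statistical testing using Shapiro-Wilks". A second check follows: "Continuous data will be plotted and assessed for normality". The method depends on the answer. "Statistical testing for differences between HC and TIA groups will be by two-way ANOVA for continuous, parametric data"; the alternative is "Friedman 2 way analysis of variance for continuous, non-parametric data".

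The Synopsis gives the size: "40 participants in total; 20 participants with TIA and 20 HC". Section 11.3 sets significance at p < 0.05 and does not say whether this also governs the normality test. Sections 11.1 to 11.4 name no fixed primary method and no sensitivity analysis.

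**The concern.** The method for each parameter is decided by a normality judgement on the study's own data, and four things needed to apply that judgement are missing:

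- the unit tested (one cell, each group, pooled values or residuals);
- the rule for combining several test results;
- the cut-off for the normality test;
- which prevails when plot and test disagree.

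The natural reading of the text is that raw values are tested. The normality assumption of ANOVA concerns the residuals, which are neither named nor excluded.

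This would matter less if both routes answered the same question, but they do not. Section 11.1 presents both as tests of HC against TIA. Friedman ranks values within a block. The plan describes no matching of patients to controls, so the only block available is the participant, and ranks within a participant carry no information about that participant's group. A parameter that fails the check loses the comparison that section 4 relies on to show whether autoregulation is impaired in TIA. It also loses any group-by-condition term.

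**Working it through.** **Inputs from the document.** 20 TIA and 20 HC (Synopsis); two conditions, baseline and squat-stand (11.1), hence 2 × 2 = 4 cells of 20 per parameter; significance level 0.05 (11.3). The plan gives no figure for the behaviour of the normality test, so there is none to reproduce. The cited 11 per group for ARI (11.2) comes without an SD, cannot be checked, and is not used here.

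**Assumptions.** The 0.05 level applies to Shapiro-Wilk; all 20 values per cell are available; there is one value per participant per condition; the skewed distributions are log-normal; the plots do not overrule the test.

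**1. Truly normal parameters diverted to Friedman.** With k independent tests at 0.05, the chance of at least one rejection is 1 − 0.95^k.

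- One test: 1 − 0.95 = 5%.
- Either of two groups: 1 − 0.95² = 9.75%.
- Any of four cells: 1 − 0.95⁴ = 18.5%.

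The two conditions come from the same people, so the four tests are not independent. Simulation with within-participant correlation from 0 to 0.8 gave 17.8% to 18.5% for any-of-four, and separate runs at about 0.7 gave 19% to 20%. Correlation changes little. Requiring at least two of four cells to fail gives only 1% to 2%.

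**2. Skewed parameters flagged.** Simulated rejection by one cell of 20 was 19% at skewness 0.8 (SD of the log 0.25) and 38% at skewness 1.3 (SD of the log 0.40). If four cells were independent, any-of-four would flag

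- skewness 0.8: 1 − 0.81⁴ = 57%;
- skewness 1.3: 1 − 0.62⁴ = 85%.

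Simulation with correlated conditions gives about 54% and 82%.

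| Rule | Normal, diverted | Skewness 0.8, flagged | Skewness 1.3, flagged |
|---|---|---|---|
| One cell of 20 | 5% | 19% | 38% |
| Any of four cells | about 19% | about 54% | about 82% |

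The figures must be read along a row. The rule that diverts nearly one normal parameter in five also catches most skewness of 1.3; the rule that misses most of it diverts only one normal parameter in twenty.

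**3. What diversion does to the group comparison.** With two conditions, each participant contributes the ranks 1 and 2. Adding a constant to every TIA participant's values leaves all these ranks unchanged, so the Friedman statistic cannot respond to a group difference. Simulation agrees: with 20 per group, an assumed group difference of 1 SD and no condition effect, Friedman rejected in 4% of trials, and a t-test on participant means in 91%.

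**The case against.** The strongest reply is that the branching rule is at least written in advance, that the plots may temper a chance rejection, and that the outcomes listed in the Synopsis and section 6.2 are counts of recruitment, compliance, rejected measurements and derivable values, which the pre-test does not touch. All of this stands. It limits how serious the point is. It does not answer it, because 11.1 also commits to testing the two haemodynamic hypotheses and gives no rule for using the plots.

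A second reply is that the plan never states four tests per parameter. That also stands. For CBFv the Synopsis names a percentage change, which is one value per participant; with one test per group the diversion rate is then 9.75%. This is why the size is given as a range.

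Three stronger readings are tempting and should not be drawn.

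- A reader might infer that the method is picked largely by chance, by setting the 19% diversion beside the 19% and 38% flag rates. Those belong to different decision rules. Under any-of-four, a truly normal parameter stays with ANOVA about four times in five, and one with skewness 1.3 is flagged about as often.
- A reader might multiply further, to 1 − 0.95¹⁶ = 56% for CBFv and ARI on both sides. That is the chance of at least one rejection among 16 tests, not the chance that a given parameter is diverted, and it treats left and right measurements from the same person as independent.
- A reader might infer that the nominal 5% level no longer holds. A check with 4,000 replicates per setting, on normal and log-normal data, found two-stage type I error of 3.7% to 5.1% for the condition effect, and 5.0% to 5.8% for the group effect among parameters kept on ANOVA. There is no material inflation. The harm is a lost group comparison, not excess false positives.

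**Conclusion.** The point holds and should be put right before the data are analysed. The pre-test diverts about 5%, 10% or 19% of truly normal parameters according to a unit that the plan leaves open, and its ability to detect skew varies just as widely with that choice. Even the lowest rate matters, because a diverted parameter has no valid TIA-versus-HC test and no interaction term, and CBFv and ARI may then not be comparable with each other. A genuinely skewed parameter that the check correctly flags suffers the same loss.

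The percentages rest on the assumptions listed with the calculation, chiefly the 0.05 level for Shapiro-Wilk and full cells of 20. Section 11.4 excludes missing and spurious data, so real cells may be smaller. That Friedman blocked by participant cannot see a group difference follows from how it ranks and does not depend on those assumptions.

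**What to change.** In section 11.1:

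1. Remove the normality test as the rule for choosing the method.
2. Pre-specify one model for every continuous parameter, with group, condition and their interaction, and participant as the repeated factor. Where the parameter is already a change between conditions, the model reduces to the group comparison.
3. Check the residuals of that model rather than the raw values.
4. Name a robustness analysis for both hypotheses and report it whatever the checks show: for example, a permutation or rank-based between-group test on participant-level values, and a paired rank test for condition. Permuting group labels alone is not enough, because it does not test baseline against squat-stand.
5. State any transformation in advance. The document gives no basis for preferring a particular one for CBFv or ARI.

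Description by mean (SD) or median (IQR) can stay as planned. The cost is a few sentences and a little more analysis work, with no change to recruitment, procedures or sample size. The downside is that conclusions for a heavily skewed parameter will lean on the robustness analysis.

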8. STUDY PROCEDURES

8.1 Screening and Eligibility Assessment

Patients attending the specialist TIA clinic at University Hospitals of Leicester NHS Trust will be eligible for recruitment into the study.

Medical records will be reviewed by the direct care team to ensure participants meet the inclusion and exclusion criteria. Eligibility screening will only be undertaken by the direct clinical care team for potential participants.

Participants will be approached at their clinical consultation in the specialist TIA clinic by consultants, registrars or specialist nurses to determine study interest prior to referral to the researcher and provision of study specific information. A poster advertising the study will be displayed in the TIA clinic waiting room. Both participants with TIA, and healthy controls (those without a diagnosis of TIA) will be recruited from the clinic. Healthy spouses, friends or partners of patients with TIA will be asked if they would like to participate in the study as a healthy control subject.

TIA participants will be given a minimum of 1 hour, and a maximum of 48 hours to decide whether or not to take part in the study, but must undertake the study assessment within 7 days of their TIA.

Healthy control participants will be given a minimum of 1 hour, and a maximum of 7 days to decide whether or not to take part study. There is no time restriction on when they undertake the study assessment.

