11.2 Sample size calculation

A formal sample size calculation was not possible for this study therefore a realistic number of participants has been selected based on previous experience of similar research studies by [name], [name] and [name].

Brodie FG et al reported in 2009 that a sample of 11 patients per group will allow the detection of a difference in ARI of 2 units between groups, with 80% power at the 5% significance level.

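### Section 11.1 assigns Friedman's test to non-normal TIA-versus-control comparisons, but Friedman needs related samples, so that hypothesis has no suitable test when data are non-normal

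*Combined protocol and SAP*

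**What the plan says.** Section 11.1 sets two null hypotheses. The first is within person: haemodynamic parameters "do not differ between baseline recordings and during performance of squat-stand manoeuvres". The second is between people: the same parameters are equal in TIA patients and healthy controls.

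One sentence then assigns the tests, and it is worded for the second hypothesis only: "Statistical testing for differences between HC and TIA groups will be by two-way ANOVA for continuous, parametric data, Friedman 2 way analysis of variance". The sentence goes on to reserve Friedman for continuous data that are not normal, and gives chi-square for nominal data. Shapiro-Wilk on all data decides which branch a variable enters.

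The synopsis gives 20 TIA patients and 20 controls. On the source of controls, section 8.1 says: "Healthy spouses, friends or partners of patients with TIA will be asked if they would like to participate in the study". Neither that section nor the eligibility criteria in 7.2 and 7.3 set a matching rule or link a control to a particular patient. No Mann-Whitney test, Kruskal-Wallis test, transformation or rank-based model appears anywhere in the document.

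**The concern.** Friedman's test ranks observations within a block and asks whether the columns differ. It needs related observations in each block. Patients and controls are separate people, so the plan offers no blocks in which a TIA value and a control value sit side by side. The natural blocks are participants, with recordings as columns, and that tests the first hypothesis, not the second.

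The group comparison is central to the study. Section 4 says of it that "it is hoped that we will be able to establish if CA is impaired in patients with TIA". The same section says "squat-stand manoeuvres (SSMs) have also been shown to produce large changes in BP and thus CBFv", so a response shared by both groups is expected, at least for CBFv. Friedman picks up that shared response. Under the section 11.1 label, a significant result could be reported as a TIA-control difference when it shows only that both groups reacted to the manoeuvre. A real group difference could equally go unseen.

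**Working it through.** **Is there a stated figure to reproduce?** No figure in the plan decides this point. Section 11.2 cites an earlier study in which "a sample of 11 patients per group will allow the detection of a difference in ARI of 2 units between groups", but gives no SD and does not bear on the choice of test.

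**Could the groups be treated as related?** Section 8.1 makes spouses, partners and friends possible controls, but records no pair link and specifies no paired analysis. Friedman could be run between groups only by inventing pairs. With two columns it would then be a sign test whose answer depends on who is paired with whom. In one simulated 20 v 20 data set, 5,000 random pairings gave Friedman p-values from 0.00006 to 1.0, with 55% below 0.05. Mann-Whitney gave a single p of 0.013. The false-positive rate is not inflated by such pairing (4.1%, exact).

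**What does Friedman do with participants as blocks?** Adding a constant to every value of one group leaves all within-person ranks unchanged, whatever the distribution. In a simulated three-recording data set, adding 5 units to one whole group left chi-square at 0.65 and p at 0.72.

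**How would it behave at 20 + 20 with two recordings (baseline and squat-stand)?**

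Inputs: group sizes from the synopsis; significance level 0.05 from section 11.3. Normal data, response size r in SD units and within-person correlation ρ are assumptions, because the document gives none of them.

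1. The chance that a participant's squat-stand value exceeds baseline is p = Φ(r / √(2(1 − ρ))). For r = 0.5 and ρ = 0.8: Φ(0.5/√0.4) = Φ(0.791) = 0.785. With no response, p = 0.5.
2. The number of participants with a rise is W = Bin(20, p_TIA) + Bin(20, p_HC).
3. With two columns, Friedman's statistic is (2W − 40)²/40 on 1 df. It is significant at 0.05 when W ≤ 13 or W ≥ 27.
4. Summing the exact distribution of W over that region gives the Friedman rates. The Mann-Whitney rates come from 20,000 simulations. The table shows ρ = 0.8, with ρ = 0.5 to 0.9 in brackets.

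| Scenario | TIA-HC difference? | Friedman significant | Mann-Whitney significant |
|---|---|---|---|
| Constant shift, no response | Yes, in level | 3.9% for any shift | about 85% (squat-stand value, 1 SD shift) |
| Same 0.5 SD response in both groups | No | 97% (66–100%) | 5% (change score) |
| Same 0.25 SD response in both groups | No | 46% (21–76%) | not run |
| 0.5 SD response in TIA only | Yes, in response | 40% (19–63%) | 66% (32–91%) (change score) |
| Opposite 0.5 SD responses | Yes, large | 1.2% (0.3–2.5%) | over 99% (85–100%) (change score) |

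With three recordings and the response in the squat-stand recording only (20,000 simulations, ρ = 0.8, 0.5 SD responses), Friedman gives 5% for the constant shift, 99% for the same response, 49% for TIA only and 2% for opposite responses. The pattern is the same.

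**The case against.** The best defence is that Friedman was meant for the baseline-versus-squat-stand hypothesis and one sentence was stretched over both. That is the likeliest explanation. It does not close the gap, because the between-group hypothesis is then left with no non-parametric test at all.

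Second, on importance. The error touches only variables that fail Shapiro-Wilk, and nothing in the document shows that CBFv or ARI will fail. The outcomes in section 6.2 are feasibility counts, and the objectives in section 5 are descriptive. This limits the reach of the problem. Still, TIA versus control is a stated null hypothesis, and the non-normal branch is a planned route.

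Third, on the figures. The 97% is a correct rejection of the first null hypothesis; it becomes an error only when read as a group difference, which is how section 11.1 labels it. It also depends on the assumed response, hence the 0.25 SD row. The table uses normal data to illustrate a branch entered when data are not normal, so the specific percentages, including the Mann-Whitney powers, should not be carried over. The blindness to a constant shift needs no distributional assumption.

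Finally, the document is silent on matching rather than ruling it out. Silence is enough here, since a paired analysis would have to be specified.

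**Conclusion.** The concern holds. Followed as written, section 11.1 applies a test that does not address the TIA-versus-control hypothesis whenever the data are non-normal. The mismatch between test and design rests on no assumed number. The size does: under the assumptions above, Friedman is significant in 21% to 100% of studies with identical 0.25 to 0.5 SD responses in both groups, and in no more than 2.5% with opposite 0.5 SD responses. A constant group shift leaves it at 3.9% when there is no response. The normal branch and the feasibility counts are unaffected. It should be corrected before analysis, so that the test for the main comparison is not chosen after the data are seen.

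**What to change.** Rewrite the test sentence in section 11.1 so that each hypothesis has its own test for non-normal data:

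- **TIA versus controls:** Mann-Whitney on one pre-specified value per participant. Use a level (for example the squat-stand value) for a difference in level, or the baseline-to-squat-stand change score for a difference in response. State which applies to CBFv and which to ARI.
- **Baseline versus squat-stand, within person:** Wilcoxon signed-rank, or Friedman if more than two recordings are compared. Say whether this is run within each group or pooled, since pooling can hide opposite responses.
- State that Friedman is not used for TIA versus controls.

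To make one value per participant definite, say which recording in section 8.5 is the baseline (seated, quiet standing, or the 90-second standing periods around the squats) and how the two middle cerebral arteries are combined or chosen. As an optional clarification, name the factors of the two-way ANOVA and its within-person error term.

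The cost is protocol wording only. No new data are needed, and these tests are standard in general statistics packages.
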